## Abstract

Object name	Analysis of integrated clinical, laboratory and prognostic data of neonates with necrotizing enterocolitis
Goal of study	This retrospective cohort study aims to enroll patients with necrotizing enterocolitis (NEC) from July 1, 2017 to December 31, 2022, conduct a comprehensive analysis of their clinical characteristics, metabolic indicators, laboratory parameters, prognosis, and outcomes, and identify indicators that may predict the progression of neonatal NEC and its associated mortality.
Research design	Retrospective cohort study
Research period	July 1, 2024 to June 30, 2025
Leading unit	Guangzhou Women and Children's Medical Center
Research Consultant	[name]; [name]
Research object	Neonates with necrotizing enterocolitis (NEC) from July 1, 2017 to December 31, 2022, conduct a comprehensive analysis of their clinical characteristics, metabolic indicators, laboratory parameters, prognosis, and outcomes.
Inclusion criteria	(1) Diagnosis of NEC
Excluded criteria	Data that meets any of the following conditions need to be eliminated: (1) Congenital gastrointestinal malformations (e.g., intestinal atresia, Hirschsprung's disease) or spontaneous intestinal perforation; (2) Hereditary metabolic disorders; (3) refusal of participation.
Sample size	220 newborns who suffered from necrotizing enterocolitis between

	July 1, 2017 to December 31, 2022
Data collection	Data collection was performed via structured extraction from electronic medical records. The following variables were systematically retrieved: (1) Neonatal medical history, including sex, gestational age, birth weight, and history of birth asphyxia (e.g., Apgar scores); (2) Maternal medical history, particularly mode of delivery, chorioamnionitis, and premature rupture of membranes; (3) NEC-related clinical parameters: Bell's staging, clinical manifestations (abdominal distension, bloody stools, pneumoperitoneum), complications (patent ductus arteriosus [PDA], sepsis, shock), therapeutic interventions (mechanical ventilation, surgical treatment), and mortality; (4) CBC parameters, lactate levels, and parameters required for calculating the nSOFA score at the onset of NEC.
Statistical processing	Statistical analyses and graphic visualization were performed using SPSS 26.0 (IBM Corp.) and GraphPad Prism 9.0. Data for normally distributed, skewed distributed, and categorical variables were expressed as mean $\pm$ standard deviation, median (interquartile range), and frequency (%), respectively. Intergroup comparisons of categorical variables were conducted using the Chi-square ( $\chi^2$ ) test or Fisher's exact test, while continuous variables were analyzed using the Student's t-test or Mann-Whitney U test. Variables with $p < 0.05$ in univariate analysis were subsequently included in multivariate logistic regression analysis.  Mediation analysis was performed using the PROCESS macro 4.1, with 1000 bootstrap iterations to decompose the total effect into direct and indirect paths. Receiver operating characteristic (ROC) curve analysis was conducted using SPSS 26.0 to evaluate the predictive performance of individual and combined biomarkers. All analyses adopted two-tailed tests, and $p < 0.05$ was considered statistically significant.
Abbreviation	NEC, necrotizing enterocolitis; PNEC, perforated necrotizing

enterocolitis; VLBW, very low birth weight; SGA, small for gestational age; NICUs, neonatal intensive care units; PDA, patent ductus arteriosus; RDS, Respiratory distress syndrome; CRP, C-reactive protein; WBC, white blood cell; CBC, complete blood count; NEU, absolute neutrophil count; LYM, absolute lymphocyte count; MON, absolute monocyte count; EOS, eosinophilic granulocyte; RBC: red blood cell; PLT, platelet count; MPV, mean platelet volume; PDW, platelet distribution width; NLR, neutrophil-to-lymphocyte ratio; NMR, neutrophil-to-monocyte ratio; MLR, monocyte-to-lymphocyte ratio; SII, systemic inflammatory index =  $(NEU*PLT)/LYM$ ; SIRI, systemic inflammatory response index =  $(NEU*MON)/LYM$ ; AISI, aggregate inflammatory systemic index =  $(NEU*MON*PLT)/LYM$ ; nSOFA, neonatal sequential organ failure assessment; ROC, receiver operating characteristic; AUC, the area under the ROC curve; OR, odds ratio; CIs, confidence intervals.

## 1. project basis

### 1.1 Research background

Necrotizing enterocolitis (NEC), a life-threatening gastrointestinal disorder predominantly, affects 5–12% of very low birth weight (VLBW) neonates, with 20–40% of cases progressing to severe disease requiring surgical intervention, while survivors often endure lifelong consequences, including short-bowel syndrome and neurodevelopmental impairments [1-4]. Despite advances in neonatal care, early identification of high-risk patients remains challenging due to the nonspecificity of clinical signs (e.g., abdominal distension, feeding intolerance) and radiographic findings (e.g., pneumatosis intestinalis), which frequently manifest only after irreversible bowel damage has occurred [5]. Furthermore, current diagnostic tools or conventional biomarkers lack both sensitivity and specificity for early risk stratification of NEC, underscoring an urgent need for biomarkers that integrate pathophysiological mechanisms to guide preemptive therapeutic strategies.

Emerging evidence underscores the multifactorial pathophysiology of NEC, where intestinal ischemia-reperfusion injury, exaggerated immune activation, and microbial dysbiosis converge to drive disease progression [6]. Hypoxic-ischemic injury constitutes a key pathological mechanism underlying intestinal mucosal damage in NEC, driving dysregulation of cellular processes including apoptosis, autophagy, proliferation, and migration within intestinal tissues [7]. In infants with NEC, persistent hypoxemia and compromised tissue perfusion induce metabolic reprogramming, marked by a shift toward glycolytic dominance—a compensatory adaptation to oxygen deprivation. Within this framework, serum lactate, as a well-established marker of tissue hypoperfusion and anaerobic metabolism, has garnered attention for its prognostic relevance. Elevated lactate levels correlate with transmural intestinal necrosis and predict fatal outcomes in NEC, reflecting the severity of ischemic insult [8,9]. However, lactate alone lacks specificity, as hyperlactatemia may arise from concurrent sepsis or perinatal asphyxia, limiting its standalone utility [10,11]. Recent studies propose combining lactate with

immune-inflammatory biomarkers (such as intestinal fatty acid binding protein or albumin) to address this limitation [12,13]. Peripheral blood cell analysis serves as a widely accessible and rapid auxiliary diagnostic tool in neonatal intensive care units (NICUs). Dynamic changes in peripheral white blood cell (WBC) counts and subset distribution have been validated as biomarkers closely associated with NEC [14]. Accumulating evidence underscores the involvement of lactate metabolism in immunomodulation and its influence on disease pathogenesis [15]. However, the combined utility of lactate levels and peripheral WBC profiles for NEC diagnosis and prognostic stratification remains unexplored.

As NEC progresses, particularly in cases of perforated NEC, it can evolve from a localized intestinal disease into a systemic illness characterized by a sepsis-like state and multi-organ dysfunction. The Neonatal Sequential Organ Failure Assessment (nSOFA) score is a validated tool designed to objectively quantify the degree of organ dysfunction in critically ill neonates by evaluating the respiratory, cardiovascular, and hematologic systems [16]. Studies have demonstrated that higher nSOFA scores are strongly and independently associated with mortality risk in neonates with respiratory distress syndrome, late-onset sepsis, and NEC [16-18]. However, single nSOFA lacks sufficient sensitivity for severe NEC subtypes like PNEC-specific risk stratification: while it predicts overall NEC mortality and the need for surgical intervention [16], existing studies have not specifically evaluated its performance in distinguishing NEC from non-perforated NEC or predicting PNEC-related mortality. The Lewis et al. [16] study included surgical NEC (e.g., laparotomy or peritoneal drain placement) but did not isolate PNEC as a distinct endpoint, leaving a critical gap in understanding how nSOFA performs in this highest-risk subgroup.

## 1.2 Creativity

To address these gaps, the present retrospective cohort study aims to explore the potential predictive value of integrating metabolic (lactate), hematologic (CBC), and organ dysfunction (nSOFA) metrics for NEC and its associated mortality in preterm infants. By combining these complementary markers, we aim to overcome the

limitations of single biomarkers and fill the knowledge gap regarding risk stratification for perforated NEC—an outcome that holds profound implications for clinical decision-making and improving the survival rate of preterm infants.

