## 2. Research objective

This retrospective cohort study aims to enroll patients with necrotizing enterocolitis (NEC) from July 1, 2017 to December 31, 2022, conduct a comprehensive analysis of their clinical characteristics, metabolic indicators, laboratory parameters, prognosis, and outcomes, and identify indicators that may predict the progression of neonatal NEC and its associated mortality.

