### 3.4 Inclusion criteria

- (1) Diagnosis of NEC and having undergone surgical treatment, confirmed by clinical manifestations (e.g., abdominal distension, bloody stools), radiological evidence (pneumatosis intestinalis, portal venous gas, or pneumoperitoneum), and pathological examination in accordance with established guidelines;
- (2) Availability of complete medical records for data extraction.

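### Section 1.2 states an aim (predicting NEC, in preterm infants) that does not match the objective, eligibility and outcomes, and the analysis plan leaves gestational age to a univariate p-value

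*Combined protocol and SAP*

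**What the plan says.** Section 1.2 (Creativity) gives the aim as exploring the predictive value of combined "metrics for NEC and its associated mortality in preterm infants". Its next sentence narrows the target: the work is to "fill the knowledge gap regarding risk stratification for perforated NEC". Section 1.1 presents the combined use of lactate and white-cell profiles as a gap that "for NEC diagnosis and prognostic stratification remains unexplored".

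The formal objective in Section 2, repeated as the goal in the Abstract, is to "identify indicators that may predict the progression of neonatal NEC and its associated mortality". It mentions neither preterm infants nor the onset of NEC.

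Section 3.4 admits infants with "Diagnosis of NEC and having undergone surgical treatment"; the Abstract asks only for the diagnosis. Neither these criteria nor the exclusions in Section 3.5 set a gestational-age limit. Section 3.2 gives the sample as 220 newborns with NEC. Section 3.3 takes blood count, lactate and nSOFA data at the onset of NEC.

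Section 3.6 lists gestational age as a baseline variable and names perforated NEC and in-hospital mortality as primary outcomes. Section 3.7 carries variables with univariate p < 0.05 into multivariable logistic regression and plans ROC analyses of single and combined markers. It plans no restriction, subgroup or stratification by gestational age.

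**The concern.** There are two mismatches.

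**Target.** Read literally, Section 1.2 promises prediction of NEC, and the diagnostic gap in Section 1.1 points the same way. A cohort made up only of NEC cases holds no information on who develops NEC. If the wording stays, a report could cite it in support of a diagnostic or predictive claim about NEC that has no data behind it.

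**Population.** The aim is worded for preterm infants, but term infants are eligible. Gestational age may be related both to marker levels and to the risk of perforation or death. Where it is, a pooled analysis can understate a marker's discrimination in preterm infants, or credit a marker with discrimination that belongs to gestational age. The plan handles this only through univariate screening. A covariate can matter as a confounder and still miss p < 0.05 on its own, and ROC curves for single markers are unadjusted in any case.

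**Working it through.** The plan has no figure to reproduce. The 220 is a count of cases, with no event rate, effect size or precision target behind it. The check is mainly a comparison of sections.

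| Element | Section 1.2 | Rest of the plan |
|---|---|---|
| Population | Preterm infants | Neonates or newborns, no gestational-age limit (Sections 2, 3.2, 3.4, 3.5, Abstract) |
| Target | NEC and its mortality, then perforated NEC | Progression and mortality (Section 2); perforation and in-hospital death (Section 3.6) |
| Disease status at entry | Not stated | NEC in all 220 (Sections 3.2, 3.4) |
| Predictor timing | Not stated | Onset of NEC (Section 3.3) |
| Gestational age in the analysis | Not stated | Only if univariate p < 0.05 (Section 3.7) |

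**Step 1: what can be estimated.** NEC is present in 220 of 220, so as an outcome it does not vary and no logistic model or ROC curve for NEC versus no NEC can be fitted. The predictors are measured at onset, so they could not serve to predict onset either. Perforated versus non-perforated NEC and death versus survival can both vary within the cohort, so those analyses are possible.

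**Step 2: whose result it is.** With no age limit, the estimates describe whatever mix of term and preterm infants the hospital records supply. Gestational age is recorded, so a preterm analysis can be run, but none is planned.

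**Step 3: what determines the size of the effect.** Let e be the share of events that occur in preterm infants and n the share of non-events that occur in preterm infants. The pooled AUC is a weighted mean over event/non-event pairs:

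AUC = e·n·A(PP) + e·(1−n)·A(PT) + (1−e)·n·A(TP) + (1−e)·(1−n)·A(TT)

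Here A(PT) is the probability that a preterm infant with the event has a higher marker value than a term infant without it, and likewise for the others. The documents supply none of e, n or the four A terms.

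**Illustration only; every input below is assumed.** Take term shares of 10%, 20% and 30% (22, 44 and 66 of 220).

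(a) *Dilution.* A marker has AUC 0.75 in preterm infants and none in term infants, whose values are distributed like those of preterm non-events. The formula reduces to 0.75·e + 0.50·(1−e).
- Equal event rates: e = 0.90, 0.80, 0.70, so AUC = 0.725, 0.700, 0.675.
- Event rate 30% preterm, 10% term: e = 0.27/0.28 = 0.964, 0.24/0.26 = 0.923, 0.21/0.24 = 0.875, so AUC = 0.741, 0.731, 0.719.

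(b) *Spurious discrimination.* A marker has no value in either group but lies 0.5 to 1 SD lower in term infants, with event rates 30% and 10%. Then A(PP) = A(TT) = 0.5, A(PT) = Φ(shift/√2) and A(TP) = 1 − A(PT).
- 10% term, 0.5 SD: e = 0.964, n = 0.63/0.72 = 0.875, A(PT) = 0.638, so AUC = 0.51.
- 30% term, 1 SD: e = 0.875, n = 0.49/0.76 = 0.645, A(PT) = 0.760, so AUC = 0.56.

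For scale, the null standard error of an AUC at 20% term in (b) is √[(220+1)/(12·57.2·162.8)] = 0.044, where 57.2 = 176·0.30 + 44·0.10 events. The illustration shows that distortion can go either way and that its size depends on the assumptions. It does not estimate the bias in this study.

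**The case against.** The strongest reply is that Section 1.2 is a rationale paragraph and Section 2 is the operative objective. Section 2, the eligibility criteria and the primary outcomes agree with one another: neonates, already with NEC, followed for progression and death. The reference to predicting NEC is probably a slip for perforated NEC. The next sentence names perforated NEC, Section 1.1 seems to make the same slip when it contrasts NEC with non-perforated NEC, and no analysis of NEC occurrence is set up anywhere. Of the two mentions of preterm infants in Section 1.2, only the first is part of the aim; the second describes an expected benefit. Gestational age is collected and may enter the models through screening.

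Most of this stands. A reader might infer from Section 1.2 that the study cannot answer its stated aim. The documents do not support that: the mortality part and the perforation target can be studied in this cohort, and preterm infants can be analysed separately from data already extracted. A reader might also infer that pooling biases the results by a known amount. That is not supported either, for want of inputs.

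Two things remain. A probable slip still needs correcting, because Section 1.1 speaks of diagnosis too and a reader cannot be sure which target was intended. And adjustment that depends on a univariate p-value is not adjustment by design, and does nothing for the single-marker ROC curves.

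**Conclusion.** The point holds as an inconsistency between Section 1.2 and the rest of the plan, with one consequence for the analysis. The study can address perforation and in-hospital death among infants with NEC; it cannot address the occurrence or diagnosis of NEC. That part follows from the eligibility criteria and needs no assumption. As written, term and preterm infants would be pooled, with gestational age adjusted for only conditionally. Whether this matters in practice depends on how many of the 220 were born at term and how far event rates and marker levels differ from those of preterm infants. The documents give none of these, so no size is claimed. The defect limits interpretation and is repairable; it does not invalidate the study.

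**What to change.** 1. **Section 1.2.** Replace the aim now worded as "metrics for NEC and its associated mortality in preterm infants" with predictive value *for perforated NEC and in-hospital death among neonates with NEC*. This brings it into line with Sections 2 and 3.6. Sections 3.4 and the Abstract differ on whether surgical treatment is required; once they are reconciled, the population named in 1.2 should follow.
2. **Section 3.7, models.** Include gestational age in every multivariable and combined-marker model, whatever its univariate p-value.
3. **Section 3.7, preterm analysis.** Report the main models and ROC analyses also in infants born before 37 weeks, give the numbers of preterm and term infants with their events, and limit any conclusion about preterm infants to that analysis.

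Making preterm infants the primary analysis set is an alternative, but it trades sample size for a narrower population and is not needed to resolve the mismatch.

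The cost is one extra covariate per model and less precision in the preterm-only analysis. No new data are needed, since gestational age is already extracted.

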## 2. Research objective

This retrospective cohort study aims to enroll patients with necrotizing enterocolitis (NEC) from July 1, 2017 to December 31, 2022, conduct a comprehensive analysis of their clinical characteristics, metabolic indicators, laboratory parameters, prognosis, and outcomes, and identify indicators that may predict the progression of neonatal NEC and its associated mortality.

## 3. Research scheme and technical route

### 3.1 Research Design

The principal investigator (PI) and project leader of this study are [name], chief physician of pediatrics of the Guangzhou Women and Children's Medical Center. In this study, a retrospective analysis was conducted on 220 enrolled neonates with necrotizing enterocolitis (NEC), with data collected from July 1, 2017 to December 31, 2022. Statistical methods including correlation analysis, multivariate logistic regression, mediation analysis, and receiver operating characteristic (ROC) curve analysis were employed to perform mutual analysis of the collected clinical data, laboratory parameters, and prognostic/mortality outcomes. This analysis aimed to identify meaningful biomarkers and establish a predictive model, thereby providing evidence for the pathophysiological mechanisms underlying NEC progression. It is anticipated that this will optimize clinical decision-making for NEC patients and improve the survival rate and quality of life of these neonates.

### 3.2 Sample size

220 newborns who suffered from necrotizing enterocolitis between July 1, 2017 to December 31, 2022.

### 3.3 data collection

Data collection was performed via structured extraction from electronic medical

records. The following variables were systematically retrieved: (1) Neonatal medical history, including sex, gestational age, birth weight, and history of birth asphyxia (e.g., Apgar scores); (2) Maternal medical history, particularly mode of delivery, chorioamnionitis, and premature rupture of membranes; (3) NEC-related clinical parameters: Bell's staging, clinical manifestations (abdominal distension, bloody stools, pneumoperitoneum), complications (patent ductus arteriosus [PDA], sepsis, shock), therapeutic interventions (mechanical ventilation, surgical treatment), and mortality; (4) CBC parameters, lactate levels, and parameters required for calculating the nSOFA score at the onset of NEC.

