### 3.6 Observation items

- (1). Baseline Characteristics: Neonatal demographics (sex, gestational age, birth weight, small for gestational age [SGA] status), maternal factors (mode of delivery, premature rupture of membranes, chorioamnionitis), neonatal birth history (1-min Apgar score  $\leq 7$ , intrauterine distress), and preterm complications (patent ductus arteriosus [PDA], respiratory distress syndrome [RDS], sepsis, shock), feeding pattern, and requirement for mechanical ventilation.

- (2). Laboratory and Clinical Assessment Indicators: Hepatobiliary function:

Albumin, albumin/globulin ratio, total bile acid; Hematologic and inflammatory parameters: White blood cell (WBC), absolute neutrophil (NEU), lymphocyte (LYM), monocyte (MON), eosinophil (EOS) counts, red blood cell (RBC), platelet (PLT) count, mean platelet volume (MPV), platelet distribution width (PDW), C-reactive protein (CRP), neutrophil-to-lymphocyte ratio (NLR), monocyte-to-lymphocyte ratio (MLR), neutrophil-to-monocyte ratio (NMR), systemic inflammatory index (SII), systemic inflammatory response index (SIRI), aggregate inflammatory systemic index (AISI); Metabolic: Serum lactate, blood glucose; Organ dysfunction assessment: Neonatal Sequential Organ Failure Assessment (nSOFA) score.

(3). Primary Outcome Indicators:

- Occurrence of perforated necrotizing enterocolitis (PNEC);
- In-hospital mortality.

(4). Secondary Outcome Indicators:

- Bell's staging of NEC;
- surgical NEC

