### 3.7 Statistical processing

Statistical analyses and graphic visualization were performed using SPSS 26.0 (IBM Corp.) and GraphPad Prism 9.0. Data for normally distributed, skewed distributed, and categorical variables were expressed as mean  $\pm$  standard deviation, median (interquartile range), and frequency (%), respectively. Intergroup comparisons of categorical variables were conducted using the Chi-square ( $\chi^2$ ) test or Fisher's exact test, while continuous variables were analyzed using the Student's t-test or Mann-Whitney U test. Variables with  $p < 0.05$  in univariate analysis were subsequently included in multivariate logistic regression analysis.

Mediation analysis was performed using the PROCESS macro 4.1, with 1000 bootstrap iterations to decompose the total effect into direct and indirect paths. Receiver operating characteristic (ROC) curve analysis was conducted using SPSS 26.0 to evaluate the predictive performance of individual and combined biomarkers. All analyses adopted two-tailed tests, and  $p < 0.05$  was considered statistically

significant.

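### Postnatal age at NEC onset is in neither variable list, so the stated adjustment rule cannot separate the onset markers from age

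*Combined protocol and SAP*

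**What the plan says.** The marker time point is set in section 3.3, item (4): "CBC parameters, lactate levels, and parameters required for calculating the nSOFA score at the onset of NEC".

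The age-related variables appear in two places:
- Section 3.3, item (1): "Neonatal medical history, including sex, gestational age, birth weight, and history of birth asphyxia (e.g., Apgar scores".
- Section 3.6, item (1): "Neonatal demographics (sex, gestational age, birth weight, small for gestational age [SGA] status", followed by maternal factors, birth history, preterm complications, feeding and ventilation.

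Postnatal age, postmenstrual age and date of onset are named in neither section, nor in the abstract, which repeats 3.3. The criteria in 3.4 and 3.5 set no range for gestational age or age at onset.

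Section 3.7 gives one route into the multivariable model: variables with p<0.05 "in univariate analysis were subsequently included in multivariate logistic regression analysis". No covariate is kept regardless of its p-value, and none is named for the mediation or ROC analyses. The two primary outcomes are "Occurrence of perforated necrotizing enterocolitis (PNEC" and "In-hospital mortality". Section 3.1 also wants the results to inform the mechanism of NEC progression.

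**The concern.** A marker read at disease onset is read at whatever age the infant has reached. If neutrophil and lymphocyte counts drift with days since birth, then the counts, and the ratios and indices built from them (NLR, SII, SIRI, AISI), carry information on age. If age at onset is also related to perforation or death, it confounds every marker-outcome association. Section 1.1 offers a related reason within the plan itself: it names perinatal asphyxia as another source of raised lactate. Asphyxia is a birth event, so its share of the lactate at onset plausibly depends on the time since birth.

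At stake are the adjusted odds ratios, the split into direct and indirect effects, and the mechanistic reading in 3.1. Without age at onset, the study also cannot show that a marker adds anything to age.

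**Working it through.** **1. Is there a figure in the plan to reproduce?** No. Section 3.2 gives "220 newborns who suffered from necrotizing enterocolitis between July 1, 2017 to December 31, 2022", a case count with no event rate, effect size or power. The check therefore compares the variable lists with the adjustment rule and then sizes the possible effect under stated assumptions.

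**2. Lists against rule.** The markers are tied to onset (3.3). The two lists hold gestational age and birth weight but not age at onset (3.3, 3.6). The rule in 3.7 selects among collected variables. A variable that is not collected can neither pass nor fail the screen, so the rule as written cannot adjust for age at onset.

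**3. Inputs.**
- From the documents: n = 220; two-sided tests ("All analyses adopted two-tailed tests") at 0.05.
- Assumed: event proportion p = 0.30; marker-age correlation r = 0.3 to 0.5; age effect b = 0.3 to 0.5 log-odds per SD; no effect of the marker itself.

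**4. Hand approximation.** With age omitted, the marker picks up roughly r × b log-odds per SD. Its standard error is about 1/√(n·p·(1−p)) = 1/√(220 × 0.3 × 0.7) = 1/√46.2 = 0.147. With z = r·b/0.147, the false-positive rate is Φ(z − 1.96) + Φ(−z − 1.96).

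| r | b | r·b | z | Approximation | Simulated, age omitted | Simulated, age included |
|---|---|---|---|---|---|---|
| 0.3 | 0.3 | 0.09 | 0.61 | 9% | 8.8% | 5.6% |
| 0.4 | 0.5 | 0.20 | 1.36 | 27% | 24.3% | 5.0% |
| 0.5 | 0.5 | 0.25 | 1.70 | 40% | 37.3% | 5.0% |

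The simulated columns use 4,000 studies per row. The approximation runs slightly high because omitting a covariate shrinks a logistic coefficient. Repeat simulations gave about 8% to 38% without age.

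**5. Can gestational age stand in for onset age?** Partly. Take r = 0.4 and b = 0.5, and give gestational age its own effect of −0.5 log-odds per SD, entering by the plan's screen:
- uncorrelated with onset age: false positives about 21% to 25%;
- correlation −0.5 with onset age: about 16%;
- correlation −0.7: about 9% to 10%.

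**6. Does forcing gestational age alone cure it?** No. With an odds ratio of 1.5 per SD for each age variable, the two uncorrelated, marker-age correlation 0.5 and 30% events, false positives are 24% under the plan's screen, 26% with gestational age forced and 4.5% with both forced.

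**7. Does the p<0.05 screen on gestational age do harm by itself?** Suppose gestational age truly differs by 0.3 SD between 66 events (0.30 × 220) and 154 non-events. The noncentrality is 0.3 × √(66 × 154/220) = 0.3 × √46.2 = 2.04, and the variable fails the screen in 47% of studies (52% at 25% events, 42% at 40%). Even so, in a simulation of that rule alone, false positives were 5.5% against 5.3%. A second set, with a single measured confounder, stayed at 2% to 5%. A strong confounder usually passes, and a weak one does little damage when dropped.

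**The case against.** **The lists may be open.** Item (1) of 3.3 introduces its variables as examples, and onset must be dated to pick the right sample. A reader might infer that age at onset was never extracted. The documents support only that it is not listed and that no analysis uses it. This stands, and it also makes the fix easy.

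**The premise is external.** No section says that blood counts change with postnatal age or that age at onset relates to perforation or death. The event rate, correlation and age effect are all assumed. This stands: 8% to 38% illustrates the mechanism and does not estimate this study's error rate.

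**Collected covariates may absorb part of it.** This also stands (step 5). In some simulated configurations, where the marker followed both age variables and their influences partly offset each other, the plan's rule gave false-positive rates at or below 5%. Inflation is possible, not certain.

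**The screen on gestational age and birth weight.** A reader might infer that this screen itself turns age-dependent counts into false markers. Step 7 does not support that. The remaining fault is narrower: chance can give the PNEC and mortality models different adjustment sets, so their odds ratios are not directly comparable.

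**The aim is prediction.** Section 2 seeks indicators that may predict progression and death, and a marker that predicts partly through age is not wrong for that purpose. This limits the point but does not remove it, because 3.1 claims mechanistic evidence and 3.7 plans a mediation analysis.

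**Conclusion.** The point holds in a limited form. Age at onset is absent from both variable lists although the blood counts, lactate and nSOFA inputs are tied to onset, and the plan as written cannot adjust for it. If counts and outcome both vary with that age, a marker with no effect of its own can be declared an independent predictor or appear as a mediation path. Under the stated assumptions, this happens in about 8% to 38% of studies instead of about 5%. At correlation 0.4 and log-odds 0.5 it falls to about 9% to 16% if gestational age has its own effect, correlates −0.5 to −0.7 with onset age and enters the model. The true size here is unknown.

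The consequence falls on adjusted odds ratios, mediation, mechanistic claims and any claim that a marker adds to age. It does not invalidate prediction as such. The change is worth making; confidence in the point is medium, because the link between age, marker and outcome is assumed.

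**What to change.** - **3.3 and 3.6:** add postnatal age at NEC onset, derived as onset date minus birth date.
- **3.7:** state that postnatal age at onset, together with gestational age (or birth weight, since the two overlap), stays in every multivariable logistic model and every mediation model whatever its univariate p-value, with the same adjustment set for PNEC and for in-hospital death. Confine the p-value selection step to the candidate markers.
- **If added value over age is to be claimed:** report the ROC result for the age variables alone beside the result with the marker added.

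Forcing gestational age or birth weight serves mainly to keep the adjustment sets consistent; age at onset is what removes the confounding.

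Cost: one date subtraction per infant from the same records, and a sentence in 3.7. Section 5 schedules case collection to end in March 2025, so this may mean returning to the records for two dates. Each model uses about two degrees of freedom if each variable enters as one linear term. Event counts are not stated; at an assumed 20% to 40% there would be 44 to 88 events (0.20 × 220 to 0.40 × 220), and the room for two extra terms should be checked against the actual number.
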